Study 003: Extension of Study 002, carbidopa-levodopa in neovascular AMD

Study Design: Prospective, open-label, fixed dose

PI: [name], PhD

Protocol Version 1

Date: June 24, 2017

IND Number: 132078

ClinicalTrials.gov identifier: NCT 03197493

Overview of extension study: If a patient completes Study 002 without significant problems, and wishes to continue carbidopa-levodopa therapy, he or she may be enrolled in protocol 003, a 9-month extension. Visits will occur monthly and will have the same monitoring at each visit as in protocol 002. Anti-VEGF injections will be administered according to the standard of care, as in protocol 002, with the same criteria for injections. Measurements and procedures at each visit will be the same as in protocol 002. This will allow evaluation of the safety of carbidopa-levodopa over an entire year of treatment.

Objectives:

1. To determine whether L-DOPA-carbidopa supplementation can improve visual function, within 12 months, in patients with choroidal neovascular AMD (nAMD), by testing best-corrected visual acuity (BCVA).
2. To determine whether L-DOPA-carbidopa supplementation in daily doses, approximating those used in Parkinson's disease, is well tolerated for 12 months in our target group of patients with nAMD in one eye.
3. To determine whether L-DOPA-carbidopa supplementation can improve the anatomic findings on optical coherence tomography (OCT), within a total of 12 months, in the eye of patients with nAMD.
4. To determine whether L-DOPA-carbidopa supplementation can improve the anatomic findings on OCT, within 12 months, in the eye without nAMD.
5. To evaluate the effect of carbidopa-levodopa on anti-VEGF injections.

Inclusion Criteria:

- Completion of Protocol 002: Dose ranging study of carbidopa-levodopa.
- A diagnosis of AMD with choroidal neovascularization (CNV) in one eye.
- Normal or Dry AMD of any grade in the fellow eye.
- Age 50-85 years.
- Willingness to maintain AREDS vitamin Supplements throughout the study or remain off these supplements for the duration of the study, if not taking them prior to the study.
- Written informed consent at visit 1.

Exclusion criteria:

- Any current use of L-DOPA containing medication or dopamine agonist medication, or any planned use of any of these agents, except for study medication, during the study.
- Concurrent use of monoamine oxidase (MAO) inhibitors.
- Any eye condition, disease, or history of trauma in either eye, which can impair vision, except cataract or cataract surgery.
- BCVA worse than 20/60 in the better eye.
- nAMD in the fellow eye.
- Neurologic conditions which can impair vision.
- Parkinson's disease.
- Significant orthostatic hypotension, defined as a drop in systolic blood pressure, immediately upon changing from the supine to standing position, of >19 mmHg, or a symptomatic drop in systolic blood pressure, immediately upon changing from the supine to standing position.
- Significant ECG abnormalities, as judged by the Investigator.
- Estimated glomerular filtration rate (eGFR) < 20 ml/min.
- Liver enzymes >3 X the upper limit of normal.
- HbA₁C > 9.0.
- Any other significant lab abnormalities, as judged by the Investigator.
- Women of childbearing potential.
- Known retinal hemorrhage.
- Subjects who are not fluent in English.

Treatments:

Patients will receive open label carbidopa-levodopa 25-100 mg one tablet TID, in the morning, with supper and at bedtime for 9 months, or two tablets TID, in the morning, with supper and at bedtime for 9 months (300-600 mg of levodopa daily). This is the regimen the patient was taking at the end of protocol 002. If the patient was able to complete protocol 002 without a serious adverse event, but had bothersome symptoms in protocol 002, he or she will receive the intermediate dose (carbidopa-levodopa 25-100, 1 tablet TID) in the extension. Each patient will be evaluated at monthly (25-35 day) intervals and in conjunction be evaluated by the referring Retina Specialist who will assess whether the patient requires an anti-VEGF injection, based on clinical practice standard of care.

What are the risks of taking carbidopa-levodopa?

- Body as a whole: chest pain, feeling weak and fatigued.
- Cardiovascular: irregular heartbeat, low blood pressure, low blood pressure immediately upon standing, high blood pressure, fainting, vein inflammation and palpitations.
- Gastrointestinal: dark saliva, ulcers, loss of appetite, nausea, vomiting, diarrhea, constipation, heartburn, dry mouth, altered taste and gastrointestinal bleeding.
- Hematologic: anemia, low white blood cells, low platelets.
- Hypersensitivity: skin rash, itching, face or throat swelling.
- Musculoskeletal: back pain, shoulder pain, muscle pain.
- Nervous system/Psychiatric: delusions, hallucinations, confusion, agitation, dizziness, sleepiness, abnormal dreams, insomnia, abnormal sensations, headache, depression, abnormal movements, mental difficulties, urge to gamble, increased sexual desire, problems with impulse control.
- Respiratory: shortness of breath, upper respiratory infection.

- Skin: Rash, increased sweating, hair loss, dark sweat.
- Urogenital: urinary tract infection, urinary frequency, dark urine.

Dealing with Adverse Events:

Study Participants will be asked about any adverse events at each visit, and asked to tell the study doctor or study staff right away if they have any side effects, or if they have any other problems with their health or the way they feel during the study, regardless of whether or not they think these problems are related to the study drug. The answers will be recorded in the source documents. For minor and easily tolerated events, the participants will continue in the study, unless they request to be withdrawn from the study. For serious or poorly tolerated events, the patient will be withdrawn from the study. Appropriate medical care will be instituted for any serious adverse events.

Number of subjects: 52 completed

Duration: Up to 9 months of treatment.

Measurements and Activities:

- Written informed consent at Visit 1.
- Ophthalmic history and comprehensive eye examination; including visual acuity, with current refraction, using an EDTRS chart, in each of both eyes separately, and ophthalmoscopic examination, and SD-OCT.
- Repeat assessment of visual acuity using an EDTRS chart, ophthalmoscopic examination, and SD-OCT at monthly visits.
- Subjective Vision Questionnaire at monthly visits.
- Demographics obtained at Baseline in Study 002 or Study 001.

- Medical History, Vital Signs and Physical Examination at Baseline in Study 002 or Study 001.
- ECG, CBC, Chem 20 and HbA₁C at Baseline in Study 002 or Study 001.
- Dispense study medication at monthly visits.
- Pill count at monthly visits
- Non-directed assessment of adverse events at each visit, including classification as to severity, seriousness and body system.
- Concomitant medications at each visit.
- If a patient had the baseline evaluation in Study 001, that will be used as the baseline evaluation for this study. If the patient entered directly into Study 002, that will be used as the baseline evaluation for this study.

Criteria for repeat anti-VEGF injections:

This will be based on monthly evaluation of: BCVA (decrease of 5 letters from previous visit); increased macular thickness (compared to normal and previous visit as measured by SD-OCT); new blood (hemorrhage) on direct retinal examination; or subjective decrease in vision. If any of these criteria are met, or if, in the opinion of the Retina Specialist, the patient requires anti-VEGF therapy, the patient will have an anti-VEGF injection administered. If none of these criteria are met at monthly visits with patient agreement, an anti-VEGF injection will not be performed, and the patient will be reevaluated.

Result sharing with subjects:

After the conclusion of the study, patients will be notified of the results, regarding safety, tolerability and vision-related outcomes.

Table 1A of Study 003 Activities by Visit

	Visit 5 Extension	Visit 6	Visit 7	Visit 8	Visit 9
	25-35 Days	25-35 Days	25-35 Days	25-35 Days	25-35 Days
Informed Consent	X				
Concomitant Medications	X	X	X	X	X
Adverse Event Assessment	X	X	X	X	X
Vital Signs	X	X	X	X	X
Subjective Vision Test	X	X	X	X	X
Retinal Exam	X	X	X	X	X
BCVA (ETDRS Protocol)	X	X	X	X	X
SD-OCT Scan	X	X	X	X	X
Dispense Medication	X	X	X	X	X
Pill Count	X	X	X	X	X

Table 1B of Study 003 Activities by Visit

	Visit 10 25-35 Days	Visit 11 25-35 Days	Visit 12 25-35 Days	Visit 13 25-35 Days
Concomitant Medications	X	X	X	X
Adverse Event Assessment	X	X	X	X
Vital Signs	X	X	X	X
Subjective Vision Test	X	X	X	X
Retinal Exam	X	X	X	X
BCVA (ETDRS Protocol)	X	X	X	X
SD-OCT Scan	X	X	X	X
Dispense Medication	X	X	X	
Pill Count	X	X	X	X

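### Objective 2 asks about 12-month tolerability in the nAMD target group, but Study 003 can observe only patients who completed Study 002 and chose to continue

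*Protocol*

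**What the plan says.** Objective 2 in the protocol is to find out whether the drug, at daily doses close to those used in Parkinson's disease, "is well tolerated for 12 months in our target group of patients with nAMD in one eye". The Overview of the extension study ends with a sentence on duration: "This will allow evaluation of the safety of carbidopa-levodopa over an entire year of treatment".

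Entry is described in three places:
- Overview: "If a patient completes Study 002 without significant problems, and wishes to continue carbidopa-levodopa therapy, he or she may be enrolled in protocol 003".
- Inclusion Criteria, first item: "Completion of Protocol 002: Dose ranging study of carbidopa-levodopa". It adds no condition about problems during that study.
- Treatments: provides for patients who finished Study 002 with no serious adverse event but with troublesome symptoms. They are expected to enter.

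Other text ties the extension to the earlier studies. Objective 3 speaks of change "within a total of 12 months, in the eye of patients with nAMD". Under Measurements and Activities, "If a patient had the baseline evaluation in Study 001, that will be used as the baseline evaluation for this study"; direct entrants to Study 002 use that study's baseline. Table 1A opens at "Visit 5 Extension", so visit numbering runs on. Treatment within Study 003 lasts up to 9 months. The only patient number is "Number of subjects: 52 completed".

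**The concern.** The population named in Objective 2 is defined by disease. The population that Study 003 can observe is defined by disease and by having come through earlier treatment with the same drug. For a tolerability objective this is selection on the outcome: patients who could not tolerate the drug early are the ones most likely to be absent.

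At stake is what a 12-month result can be said to show. If the objective is answered from Study 003 entrants as worded, a rate conditional on completing Study 002 would be read as the rate for patients with nAMD in one eye who start the drug. That reading would be too favourable if early intolerance occurred.

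**Working it through.** **Step 1. Time span.** The objective covers 12 months and the extension up to 9, so about 12 − 9 = 3 months must come from before Study 003. The carried-over baseline, the continuing visit numbers and the total in Objective 3 support this. The spans are consistent for a patient who enters Study 003.

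**Step 2. Who is observed over the earlier months.** Take the loosest entry wording, completion of Study 002. Every entrant has by definition finished the earlier period, some of them with symptoms. A patient who stopped Study 002 for intolerance cannot enter, and a patient who declines to go on does not. The linking text in Step 1 joins up time for entrants and brings in no one else.

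**Step 3. Is there a figure to reproduce?** No. The protocol gives no tolerability rate, no loss rate and no basis for the number 52. What follows is illustration, and every input is an assumption.

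**Step 4. Formula.** Among all who start the drug, let
- q = share lost for intolerance before roll-over
- o = share not continuing for other reasons
- T = share of entrants who tolerate the drug to month 12
- U = share of the group o who would have tolerated it

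Rate among starters = (1 − q − o)T + oU.

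Excess of the entrants' rate = T − [(1 − q − o)T + oU] = qT − o(U − T).

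**Step 5. Numbers, with T = 90%.** Excess in percentage points:

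| Assumption on the group o | q = 0% | q = 5% | q = 10% | q = 20% |
|---|---|---|---|---|
| U = T (any o) | 0 | 4.5 | 9 | 18 |
| o = 20%, U = 100% | −2 | 2.5 | 7 | 16 |
| o = 20%, U = 70% | 4 | 8.5 | 13 | 22 |

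Example, first row, q = 10%: 0.10 × 0.90 = 0.09, so 90% among entrants corresponds to 81% among starters. Second row, q = 10%: 0.10 × 0.90 − 0.20 × (1.00 − 0.90) = 0.09 − 0.02 = 0.07.

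**Step 6. When the direction reverses.** The excess is negative only if q < o(U − T)/T. With U = 100% and o = 20%, that is q < 0.20 × 0.10/0.90 = 2.2% for T = 90%, and q < 0.20 × 0.20/0.80 = 5% for T = 80%. So the entrants' rate is too high unless early intolerance is rare and those leaving for other reasons would have done better than entrants.

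**The case against.** Objectives are usually written by disease, with eligibility saying who is studied. The title calls this an extension, and both the Overview and the first inclusion criterion state the restriction openly. Objective 2 is a question and not a conclusion. This is fair, and it keeps the point to a mismatch of wording. It does not remove it, because no analysis of Study 003 entrants alone can supply patients lost to early intolerance. The population of an objective is protocol content.

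Several stronger readings are tempting, and the document does not support them:
- **The Overview's one-year sentence claims the whole target group.** It names no population and closes a paragraph that opens with the selection rule.
- **Only patients free of significant problems are enrolled.** The inclusion list asks only for completion, and Treatments provides for completers with symptoms. This softens the selection but does not end it.
- **The protocol is defective because it does not say how non-continuers are counted.** Analysis sets and denominators are commonly left to a statistical analysis plan, which is not among the documents.
- **The number 52 restricts the analysis to completers.** It is a target count; adverse events are collected from every participant at each visit.
- **A bias has been shown.** All four inputs in the illustration are assumed, and the results include zero and a reversed sign. How many patients stopped earlier depends on studies not described here.

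**Conclusion.** The mismatch stands. Objective 2 names the nAMD target group, while Study 003 observes a group that has already come through treatment with the drug and elected to go on. Its 12-month tolerability rate is conditional on completing Study 002.

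The direction is conditional too: the rate is too favourable for the target group if patients were lost earlier for intolerance, and if those who left for other reasons would not have tolerated the drug much better than entrants. The size cannot be known from the document. The 4.5, 9 and 18 points for assumed early losses of 5%, 10% and 20% rest on T = 90% and U = T, and show only that the difference could be large enough to matter. The matter should be fixed, and confidence is moderate.

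**What to change.** Choose one of two changes to Objective 2.

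1. Restate it as tolerability among patients who completed Study 002 and continued. Report results for the extension period, or over 12 months but explicitly conditional on completing Study 002. Give the Overview's one-year sentence the same qualifier. This costs a few words and a narrower claim.
2. If the 12-month question for the target group is kept, state that it is assessed from the first dose in all patients who started the drug in the parent study or studies (Study 002, and Study 001 if the drug was given there, which this document does not say). Count discontinuation or non-roll-over for intolerance as an event. This costs one pooled analysis and possibly a less favourable figure.

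Under either choice it helps to report numbers and reasons at each step: started, completed Study 002, did not roll over, entered Study 003, withdrew, completed.

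Separately, the entry wording in the Overview, the inclusion list and Treatments differs and must be reconciled. Which rule should apply is for the sponsor to decide.

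### Objectives 1, 3, 4 and 5 ask for an effect of levodopa that an uncontrolled open-label extension cannot show; selection also narrows Objective 2 and the one-year safety aim

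*Protocol*

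**What the plan says.** **Objectives.** Objective 1 is "To determine whether L-DOPA-carbidopa supplementation can improve visual function, within 12 months, in patients with choroidal neovascular AMD (nAMD), by testing best-corrected visual acuity". It names no eye, and Measurements and Activities has acuity tested in each eye separately. Objective 3 is "To determine whether L-DOPA-carbidopa supplementation can improve the anatomic findings on optical coherence tomography (OCT), within a total of 12 months", for the eye with nAMD. Objective 4 puts the same question for the eye without nAMD. Objective 5 is "To evaluate the effect of carbidopa-levodopa on anti-VEGF injections". Objective 2 concerns tolerability over 12 months.

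**Design.** The study is described as "Prospective, open-label, fixed dose". Under Treatments, all patients receive carbidopa-levodopa at one of two levels. On the level, the protocol says "This is the regimen the patient was taking at the end of protocol 002"; a patient who completed without a serious adverse event "but had bothersome symptoms in protocol 002, he or she will receive the intermediate dose".

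**Entry and baseline.** The Overview opens entry to a defined group: "If a patient completes Study 002 without significant problems, and wishes to continue carbidopa-levodopa therapy". Measurements and Activities takes the baseline evaluation from Study 001 if the patient had it there, and otherwise from Study 002.

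**Anti-VEGF.** Under the criteria for repeat injections, any one of these suffices: a 5-letter fall in BCVA from the previous visit, increased macular thickness on SD-OCT, new haemorrhage, a subjective decrease in vision, or the Retina Specialist's opinion that treatment is required.

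**What the design is said to allow.** The Overview names safety only: "This will allow evaluation of the safety of carbidopa-levodopa over an entire year of treatment".

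**The concern.** Objectives 1, 3, 4 and 5 are causal questions. To answer them, the study needs something that shows what would have happened to BCVA, OCT and injections without levodopa. If nothing does, a change from baseline combines levodopa with natural course, selection and, in the nAMD eye, anti-VEGF.

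The wording invites a gain to be read as a levodopa benefit, or a flat result as no benefit, when neither follows. Four of the five objectives are affected. The protocol also promises to tell patients the vision-related outcomes, so the interpretation will reach people who cannot judge the design for themselves.

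**Working it through.** The main check sets the passages side by side.

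**1. Is there a comparison within the study?**
- *Untreated or placebo group:* none is described, and all patients take levodopa.
- *Dose level:* it is carried over from Study 002 or set by symptoms there. The two groups therefore differ in tolerability as well as dose.
- *Fellow eye:* the drug is oral, so this eye is exposed too. Because nAMD in the fellow eye is an exclusion, it also does not have the same disease.
- *Own baseline:* this is the only reference the protocol fixes. That BCVA and OCT change will be measured from it is an inference from the baseline rule and the 12-month horizon; the protocol does not say so expressly.

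**2. What stands between change and attribution, by objective?**

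| Outcome | Missing control, selection | Further problem |
|---|---|---|
| nAMD-eye BCVA (part of Obj. 1) | yes | anti-VEGF triggered by BCVA and OCT |
| nAMD-eye OCT (Obj. 3) | yes | the same |
| Fellow-eye BCVA (part of Obj. 1) | yes | none directly |
| Fellow-eye OCT (Obj. 4) | yes | none directly |
| Injections (Obj. 5) | yes | no masking described, and specialist opinion alone suffices to inject |

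In the nAMD eye, a real benefit could appear as fewer injections with flat acuity. Equally, stable acuity could be held up by injections with no benefit from levodopa.

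**3. When does selection occur?** The horizon is 12 months and the extension lasts 9. If the 12 months start in Study 002, 12 − 9 = 3 months have been observed before a patient enters. For patients who keep a Study 001 baseline, the interval depends on a study that is not at hand. All that can be said for everyone is that part of the follow-up precedes selection.

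**4. Illustration of size.** The protocol gives 52 completed subjects and states no test, SD, significance level or effect size. Everything below except n = 52 is assumed: a one-sample t test of 12-month BCVA change against zero, two-sided 5%, SD of change 8 to 15 letters.

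- Critical value: t(0.975, 51 df) = 2.008.
- Smallest significant mean gain: 2.008 × SD / √52.
- Probability of a significant gain: upper tail of the noncentral t with 51 df and noncentrality (mean shift) × √52 / SD. Example: shift 3, SD 8 gives 3 × 7.211 / 8 = 2.70 and probability 0.756.

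| SD (letters) | Smallest significant gain | No levodopa effect, background +3 | No levodopa effect, background 0 | No levodopa effect, background −1 | True +3 with background −1 (net +2) |
|---|---|---|---|---|---|
| 8 | 2.23 | 0.756 | 0.025 | 0.0022 | 0.424 |
| 10 | 2.78 | 0.565 | 0.025 | 0.0038 | 0.293 |
| 12 | 3.34 | 0.424 | 0.025 | 0.0054 | 0.218 |
| 15 | 4.18 | 0.293 | 0.025 | 0.0075 | 0.155 |

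The +3 column also gives the chance of showing a true 3-letter effect with no background shift. A 1-letter background loss would therefore cut that chance from 0.756 to 0.424 at SD 8, and from 0.293 to 0.155 at SD 15. No figure is offered for Objective 5, since it would need an assumed injection rate and within-patient correlation.

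**The case against.** The best defence is that the protocol is open about what it is. It calls itself an open-label extension, claims only a safety evaluation in the Overview, and sets no efficacy hypothesis, test or success criterion. On that view the objectives are loosely worded, and misreading them is only a prediction. The SAP, not shown here, may also hold a reference injection rate or an adjusted analysis.

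Part of this stands. The absence of such an analysis from the protocol is not a finding. Recording the reason for each injection is a form detail and carries no weight. But an external rate or an adjustment would not create a concurrent control, and the causal wording is in the protocol itself. The Overview's modest claim supports the point, because the objectives go beyond it.

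Four stronger readings are tempting, and the documents do not support them:
- *The injection triggers confound every efficacy objective.* They bear on the nAMD eye in Objectives 1 and 3. Fellow-eye nAMD is excluded, so they do not apply directly there. For Objective 5 the injection is the outcome, and the listed criteria, the same as in Study 002, partly standardise it.
- *Three of the 12 months precede selection for everyone.* This is not established for patients with a Study 001 baseline.
- *The design is biased towards showing a benefit.* Nothing in the protocol fixes the direction, and the illustration runs both ways.
- *Tolerability and safety are untouched.* Entry requires completing Study 002 without significant problems and wishing to continue, which is selection on tolerability. It is not absolute, since patients with bothersome symptoms may still enter at the intermediate dose.

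**Conclusion.** The point holds. Objectives 1, 3, 4 and 5 claim a property that the design lacks: attribution of change to levodopa. This follows from the protocol's own text and does not depend on any figure.

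Objective 2 and the one-year safety aim remain answerable, but only as tolerability and safety among patients who tolerated Study 002 well enough to complete it and chose to go on.

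The size of the bias cannot be derived from the document. The rejection probabilities are an illustration built on an assumed test, SD and background shift. A reader might take 0.76 to 0.29 as this trial's false-positive rate. It is not, because the protocol states no such test and gives no background shift.

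The problem should be fixed: the change costs little and alters what the trial may conclude.

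**What to change.** 1. Reword Objectives 1, 3, 4 and 5 as descriptive: change in BCVA and OCT, by eye, from the Study 001 or 002 baseline, and injection frequency, during levodopa given with as-needed anti-VEGF, without attribution to levodopa.
2. State in Objective 2 that it applies to patients who completed Study 002, and read the one-year safety aim in the same way.
3. Report nAMD-eye BCVA and OCT change alongside the injections received.

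The cost is the wording of five objectives and one reporting line. No visit, test, dose or injection rule changes. The downside is a weaker efficacy conclusion, which is all that this design supports.

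### A serious or poorly tolerated event ends study participation, not only dosing, and no follow-up visit exists, so the event's outcome and all later data go uncollected

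*Protocol*

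**What the plan says.** The section Dealing with Adverse Events sets two paths. Patients with minor, easily tolerated events stay in the study unless they ask to leave. For the rest, "For serious or poorly tolerated events, the patient will be withdrawn from the study". The only further step is clinical: "Appropriate medical care will be instituted for any serious adverse events".

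Safety data come from study visits: "Non-directed assessment of adverse events at each visit, including classification as to severity, seriousness and body system". Patients are also asked to report problems promptly between visits, but only while they are in the study. Measurements and Activities ties visual acuity, ophthalmoscopy and SD-OCT to the monthly visits, and the injection criteria are applied at the monthly evaluation. Tables 1A and 1B cover Visits 5 to 13 and nothing else.

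The Overview states the purpose: "This will allow evaluation of the safety of carbidopa-levodopa over an entire year of treatment". Objective 2 asks whether treatment "is well tolerated for 12 months in our target group of patients with nAMD in one eye". Objectives 1, 3 and 4 also refer to 12 months, and Objective 5 concerns anti-VEGF injections. The sample size is given as "Number of subjects: 52 completed".

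**The concern.** Stopping a drug and leaving a study are different events, and the protocol has only the second. A patient who develops, say, hallucinations, fainting or gastrointestinal bleeding (all in the protocol's own risk list) should probably stop carbidopa-levodopa. Nothing about that requires observation to end. Yet under the rule the protocol names no occasion on which to record whether the event resolved, whether another followed, or what happened to vision, retinal anatomy and injection need.

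For a study meant to describe safety over a year, these are among the patients whose course matters most. The missing 12-month values would also not be scattered at random, because an adverse event decides who has them. An analysis plan can choose how to treat missing values, but it cannot recover visits that were never held.

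**Working it through.** The protocol states no figure to reproduce for this point. The check is first textual, then a count of what the rule removes.

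**1. Is there any collection after withdrawal?**

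| Data | When the protocol collects it | Provision after withdrawal |
|---|---|---|
| Triggering event | When reported, or at the visit | Already recorded, with severity, seriousness and body system |
| Outcome of that event | Not named | None; medical care is promised for serious events only, and is not data collection |
| Later adverse events | Each visit, or reported during the study | None |
| BCVA, SD-OCT, retinal exam | Monthly visits | None |
| Injection need | Monthly evaluation | None |

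The protocol does not say outright that there is no off-drug follow-up. That is read from the text and from the two visit tables, which have no column for it.

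**2. Scheduled data lost per patient.** Inputs: Visits 5 to 13, spaced 25 to 35 days apart. Seven table rows do not depend on taking the drug: concomitant medications, adverse events, vital signs, subjective vision test, retinal exam, BCVA and SD-OCT. If the patient is withdrawn at Visit v, after that visit's assessments:

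- visits lost = 13 − v
- days lost = 25 × (13 − v) to 35 × (13 − v)
- assessments lost = 7 × (13 − v)

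| Withdrawn at | Visits lost | Days lost | Assessments lost |
|---|---|---|---|
| Visit 6 | 13 − 6 = 7 | 175 to 245 | 49 |
| Visit 9 | 13 − 9 = 4 | 100 to 140 | 28 |
| Visit 12 | 13 − 12 = 1 | 25 to 35 | 7 |

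The last column counts lost observations. It does not measure harm to any conclusion.

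**3. How many patients?** The protocol gives no rate. As an assumption only, suppose a share w of entrants leaves and every one of them leaves under this rule. Reaching 52 completers then needs 52 / (1 − w) entrants, rounded up:

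| w | Entrants | Without later data |
|---|---|---|
| 5% | 52 / 0.95 → 55 | 3 |
| 10% | 52 / 0.90 → 58 | 6 |
| 20% | 52 / 0.80 = 65 | 13 |
| 30% | 52 / 0.70 → 75 | 23 |

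**4. Bias in a 12-month mean?** If completers and withdrawn patients would differ by d letters, a mean over completers alone differs from the mean over all entrants by w × d. For illustrative d of 2 to 10 letters, that is 0.2 to 1.0 letters at w = 10% and 0.6 to 3.0 letters at w = 30%. The protocol supplies neither w, nor d, nor the sign of d, so this shows how the bias would scale and is not an estimate.

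**The case against.** The strongest reply is that this is an openly uncontrolled extension for patients who came through Study 002 and want to continue. Its stated safety aim is on-treatment, and Objectives 1, 3 and 4 ask what the drug can do within 12 months. With no comparison arm, acuity measured months after stopping says little about that. Preferring data on all entrants regardless of treatment is then a reviewer's choice rather than the correction of an error.

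Much of this stands, and it rules out several stronger readings that a reader might draw from the rule:

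- **Tolerability cannot be assessed.** Not so. The event that ends participation is itself the tolerability failure, and it can be counted among all entrants without any later visit.
- **The 12-month results describe only patients who tolerated the drug.** The protocol does not restrict the analysis to completers. The 52 is a recruitment target, and monthly data before withdrawal exist for everyone and can be used.
- **Those lost are the patients who tolerate the drug worst.** The rule covers any serious event, related or not, so this is only partly true.
- **BCVA results are flattered by a calculable amount.** It is tempting to take d = 5 letters from the re-injection criterion "BCVA (decrease of 5 letters from previous visit", but that is a visit-to-visit trigger within one patient. It does not compare withdrawn patients with completers. The listed drug risks include no loss of visual acuity, so even the direction is open.

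The reply does not answer the safety gap. The outcome of an event that began on treatment belongs to the safety of that treatment, and the protocol does not provide for recording it. Nor does it help that an investigator might follow the patient anyway, or that the referring retina specialist will go on treating the eye: the protocol names no route by which that information reaches the study.

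**Conclusion.** The point holds in a limited form. As written, the rule ends observation together with treatment, and nothing elsewhere in the protocol restores it. For each affected patient the event's outcome, later adverse events, and later BCVA, SD-OCT and injection data are lost. That means between 1 and 7 scheduled visits for withdrawals from Visit 12 back to Visit 6. The loss falls on a group selected by adverse events and weakens the one-year safety aim most directly.

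The number of patients affected is unknown. It may be small, since all entrants have already completed Study 002, although the Treatments section also admits patients who had bothersome symptoms there. No size or sign of efficacy bias can be claimed. The conclusion assumes that the rule is applied as written and that no follow-up outside the protocol feeds into the study data. It does not invalidate the study, but the loss is avoidable and cannot be repaired afterwards, so the sentence should be changed.

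**What to change.** Replace the withdrawal sentence with text to this effect:

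> A patient with a serious or poorly tolerated event stops study medication. The Visit 13 assessments are done at the stop, the date and reason are recorded, and the event is followed until it resolves or stabilises, by telephone if the patient declines visits. If willing and medically able, the patient attends the remaining scheduled visits through Visit 13 without study drug. A patient may leave the study on request, or when the investigator judges this medically necessary.

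Three consequences should be written in with it:

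- Count each such stop as a tolerability failure among all entrants under Objective 2.
- Flag off-drug visits by stop date, so that on-drug and all-entrant summaries can be separated.
- Report the number who entered and the number who stopped beside the 52. Keep the 52 as patients who finish on drug, so that attending Visit 13 off drug does not change its meaning.

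The cost is a short amendment, one assessment at the stop (an extra visit if the stop falls between scheduled ones), and off-drug visits or calls for those who stop. The off-drug visits use slots already in Tables 1A and 1B, at most 13 − 5 = 8 per patient. For patients aged up to 85 who have just had a bad event that can be a real burden, which is why those visits depend on willingness and medical fitness. The stop assessment and the follow-up of the event are the minimum to keep.
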